5.2.6. Subgroup Analyses

The planned efficacy analyses will be repeated for each subgroup.

5.3. SAFETY

5.3.1. Adverse Events

Adverse events will be mapped to a Medical Dictionary for Regulatory Activities (MedDRA) version 18.0 or higher preferred term and system organ classification. The severity of all AEs will be assessed

by the investigator according to the protocol and the CTCAE v 4.03 criteria. If a subject experiences multiple events that map to a single preferred term, the greatest severity grade and strongest investigator assessment of relation to study medication will be assigned to the preferred term for the appropriate summaries. Should an event have a missing severity or relationship, it will be classified as having the highest severity and/or strongest relationship for the purposes of summary analyses. For presentation in the data listings, the missing values will be noted. The occurrence of TEAEs will be summarized by phase (induction vs maintenance) using preferred terms, system organ classifications, and severity. Separate summaries of treatment-emergent SAEs, TEAEs related to Vicinium, TEAEs leading to discontinuation of study or study drug, serious TEAEs, and Grade 3 or higher TEAEs will be generated. All AEs reported will be listed for individual subjects showing both verbatim and preferred terms. Missing onset dates will be imputed as previously outlined in Section 3.3.5 as required to determine treatment-emergent events.

Summaries of TEAEs, TEAEs related to Vicinium, Serious TEAEs, and Grade 3 or higher TEAEs will also be presented by each subgroup.

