- Grade 3: Severe or medically significant but not immediately life-threatening; hospitalization or prolongation of hospitalization indicated; disabling; limiting self-care ADL\*\*.
- Grade 4: Life-threatening consequences; urgent intervention indicated.
- Grade 5: Death.

*A semicolon indicates “or.”*

*\*Instrumental ADL refer to preparing meals, shopping for groceries or clothes, using the telephone, managing money, etc.*

*\*\*Self care ADL refer to bathing, dressing and undressing, feeding self, using the toilet, taking medications, and not bedridden.*

Assessment of the relationship of the AE to the study drug by the investigator will be based on the following two definitions:

- Not related: A not-related AE is defined as an AE that is not associated with the study drug and can with certainty, be attributed to another cause.
- Related: A related AE is defined as an AE where a causal relationship between the event and the study drug is a reasonable possibility. A reasonable causal relationship is meant to convey that there are facts (evidence such as dechallenge/rechallenge) or other clinical arguments to suggest a causal relationship between the AE and study drug.

If discernible at the time of completing an AE eCRF, a specific disease or syndrome rather than individual associated signs and symptoms should be identified by the Investigator and recorded on the appropriate AE eCRF. However, if an observed or reported sign, symptom, or clinically significant laboratory anomaly is not considered by the Investigator to be a component of a specific disease or syndrome, then it should be recorded as a separate AE on the appropriate AE eCRF.

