3.3.7. Definitions and Terminology

Adverse Event

An adverse event (AE) is defined as any unfavorable and unintended sign (including an abnormal laboratory finding), symptom or disease temporally associated with the use of a medical treatment or procedure regardless of whether it is considered related to the medical treatment or procedure (attribution of unrelated, unlikely, possible, probable, or definite).

Any medical condition that is present at the time the subject is screened, but does not deteriorate, should not be reported as an AE. However, if it deteriorates at any time during the study it should be recorded as an AE. Hospitalization for elective treatment of a preexisting condition that did not worsen from baseline is not considered an AE or serious AE (SAE).

The descriptions and grading scales found in the revised National Cancer Institute Common Terminology Criteria for Adverse Events (NCI-CTCAE) version 4.03 will be utilized for AE reporting.

Serious Adverse Event

A serious adverse event is any AE that is fatal, life-threatening, requires or prolongs hospital stay, results in persistent or significant disability or incapacity, results in a congenital anomaly or birth defect, or is an otherwise important medical event.

Treatment-emergent AE

Treatment-emergent AEs (TEAEs) are all AEs occurring on or after the date of first dose of study drug through 30 days post the last dose of study drug.

Baseline Value

For purposes of analysis, the baseline value is defined as the last value obtained prior to the first dose of Vicinium.

Study Drug

For the purposes of this study, the term study drug refers to Vicinium.

Day 1 (Baseline)

Day 1 is the day that the first dose of Vicinium is received.

Age

The age of a subject is defined as (Date of Informed Consent – Date of Birth + 1)/365.25.

Study Day

Study Day is defined relative to Baseline (Day 1). Thus, the study day of an event is calculated as:

$$\text{Study Day} = \text{event date} - \text{date of Day 1} + 1.$$

Change from Baseline

Change from baseline for a given endpoint is defined as the Study Day X value minus the Baseline Value.

Cohort 1 Subjects

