10. PROPOSED TABLES, LISTINGS, AND FIGURES DSMB ANALYSES

Summary Tables

Table 1 Eligibility, Enrollment, and Treatment Status, All Consented Subjects

Table 2 Subject Termination from Study, Safety Population

Table 3 Demographics, Safety Population

Table 4 Baseline Disease Characteristics, Safety Population

Table 5 Treatment-Emergent Adverse Events by System Organ Classification, Preferred Term, and Greatest Severity, Safety Population

Table 6 Treatment-Emergent Adverse Events Related to Vicinium by System Organ Classification, Preferred Term, and Greatest Severity, Safety Population

Table 7 Treatment-Emergent Serious Adverse Events by System Organ Classification, Preferred Term, and Greatest Severity, Safety Population

Table 8 Clinical Laboratory Assessments by Visit, Safety Population

Table 9 Graded Laboratory Toxicities, Safety Population

Table 10 Worst Post-Baseline Laboratory Shifts, Safety Population

Table 11 Vital Signs, Weight, and Height by Visit, Safety Population

Table 12 Electrocardiogram by Visit, Safety Population

Table 13 Summary of Complete Response by Visit, Ongoing Subjects Are Excluded as 'Missing', mITT Population

Data Listings

Listing 1 Study Completion, Safety Population

Listing 2 Demographics, Safety Population

Listing 3 Adverse Events, Safety Population

Listing 3.1 Serious Adverse Events, Safety Population

Listing 4.1.1 Select Chemistry Results for Subjects with a Post-Baseline Abnormality, Safety Population

Listing 4.1.2 Clinical Chemistry Laboratory Data, Safety Population

Listing 4.2.1 Select Hematology Results for Subjects with a Post-Baseline Abnormality, Safety Population

Listing 4.2.2 Hematology Laboratory Data, Safety Population

Listing 4.3.1 Select Urinalysis Results for Subjects with a Post-Baseline Abnormality, Safety Population

Listing 4.3.2 Urinalysis Laboratory Data, Safety Population

Listing 5 Study Drug Administration, Safety Population

Listing 6 Efficacy Assessments, Safety Population

Listing 7 Vital Signs, Height, and Weight, Safety Population

Listing 8 Electrocardiogram, Safety Population

Listing 9 BCG Treatment History, Enrolled Population

Figures

Figure 1 Clinical Laboratory Assessments by Visit, Safety Population: Subjects with a Treatment Emergent Grade 3 or Higher Event

Figure 2.1 Alanine Aminotransferase (IU/L) by Visit vs. Baseline, Safety Population

Figure 2.2 Alkaline Phosphatase (IU/L) by Visit vs. Baseline, Safety Population

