- 14.2.7.1.6 Overall Survival by Prior BCG Therapies Subgroup – mITT Population
- 14.2.7.1.7 Overall Survival by Instillation Subgroup – mITT Population
- 14.2.7.3 Overall Survival – Evaluable Population
- 14.2.7.4 Overall Survival – Induction Phase Dosing Compliant Population
- 14.2.7.5 Overall Survival – Study Dosing Compliant Population

Safety

- 14.3.1.1.1 Treatment-Emergent Adverse Events by System Organ Classification, Preferred Term, and Greatest Severity
- 14.3.1.1.2 Treatment-Emergent Adverse Events By System Organ Classification, Preferred Term, and Greatest Severity – Age Subgroup
- 14.3.1.1.3 Treatment-Emergent Adverse Events By System Organ Classification, Preferred Term, and Greatest Severity – Gender Subgroup
- 14.3.1.1.4 Treatment-Emergent Adverse Events By System Organ Classification, Preferred Term, and Greatest Severity – Region Subgroup
- 14.3.1.1.5 Treatment-Emergent Adverse Events By System Organ Classification, Preferred Term, and Greatest Severity – Race Subgroup
- 14.3.1.1.6 Treatment-Emergent Adverse Events By System Organ Classification, Preferred Term, and Greatest Severity – Prior BCG Therapies Subgroup
- 14.3.1.1.7 Treatment-Emergent Adverse Events By System Organ Classification, Preferred Term, and Greatest Severity – Instillation Subgroup
- 14.3.1.2.1 Treatment-Emergent Adverse Events Related to Vicinium By System Organ Classification, Preferred Term, and Greatest Severity
- 14.3.1.2.2 Treatment-Emergent Adverse Events Related to Vicinium By System Organ Classification, Preferred Term, and Greatest Severity – Age Subgroup
- 14.3.1.2.3 Treatment-Emergent Adverse Events Related to Vicinium By System Organ Classification, Preferred Term, and Greatest Severity – Gender Subgroup
- 14.3.1.2.4 Treatment-Emergent Adverse Events Related to Vicinium By System Organ Classification, Preferred Term, and Greatest Severity – Region Subgroup
- 14.3.1.2.5 Treatment-Emergent Adverse Events Related to Vicinium By System Organ Classification, Preferred Term, and Greatest Severity – Race Subgroup
- 14.3.1.2.6 Treatment-Emergent Adverse Events Related to Vicinium By System Organ Classification, Preferred Term, and Greatest Severity – Prior BCG Therapies Subgroup
- 14.3.1.2.7 Treatment-Emergent Adverse Events Related to Vicinium By System Organ Classification, Preferred Term, and Greatest Severity – Instillation Subgroup

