- 14.3.1.3 Treatment-Emergent Adverse Events Leading to the Discontinuation of Study Drug by System Organ Classification, Preferred Term, and Greatest Severity
- 14.3.1.4.1 Treatment-Emergent Serious Adverse Events by System Organ Classification, Preferred Term, and Greatest Severity
- 14.3.1.4.2 Treatment-Emergent Serious Adverse Events by System Organ Classification, Preferred Term, and Greatest Severity – Age Subgroup
- 14.3.1.4.3 Treatment-Emergent Serious Adverse Events by System Organ Classification, Preferred Term, and Greatest Severity – Gender Subgroup
- 14.3.1.4.4 Treatment-Emergent Serious Adverse Events by System Organ Classification, Preferred Term, and Greatest Severity – Region Subgroup
- 14.3.1.4.5 Treatment-Emergent Serious Adverse Events by System Organ Classification, Preferred Term, and Greatest Severity – Race Subgroup
- 14.3.1.4.6 Treatment-Emergent Serious Adverse Events by System Organ Classification, Preferred Term, and Greatest Severity – Prior BCG Therapies Subgroup
- 14.3.1.4.7 Treatment-Emergent Serious Adverse Events by System Organ Classification, Preferred Term, and Greatest Severity – Instillation Subgroup
- 14.3.1.5.1 Treatment-Emergent Adverse Events by System Organ Classification, Preferred Term, and Severity Group
- 14.3.1.5.2 Treatment-Emergent Adverse Events Occurring in at Least 5% of Subjects by System Organ Classification, Preferred Term, and Severity Group

- 14.3.1.5.3 Treatment-Emergent Adverse Events Occurring in at Least 3% of Subjects by System Organ Classification, Preferred Term, and Severity Group
- 14.3.1.5.4 Treatment-Emergent Adverse Events Occurring in at Least 2% of Subjects by System Organ Classification, Preferred Term, and Severity Group
- 14.3.1.6.1 Treatment-Emergent Adverse Events Related to Vicinium by System Organ Classification, Preferred Term, and Severity Group
- 14.3.1.6.2 Treatment-Emergent Adverse Events Related to Vicinium Occurring in at Least 5% of Subjects by System Organ Classification, Preferred Term, and Severity Group
- 14.3.1.6.3 Treatment-Emergent Adverse Events Related to Vicinium Occurring in at Least 3% of Subjects by System Organ Classification, Preferred Term, and Severity Group
- 14.3.1.6.4 Treatment-Emergent Adverse Events Related to Vicinium Occurring in at Least 2% of Subjects by System Organ Classification, Preferred Term, and Severity Group
- 14.3.1.7 Treatment-Emergent Serious Adverse Events by System Organ Classification, Preferred Term, and Severity Group

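### SAP 5.3.1 takes greatest severity and strongest relationship separately within a preferred term, so the related-by-severity tables can show a Grade 3+ Vicinium-related entry that matches no single event

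*SAP*

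**What the plan says.** SAP Section 5.3.1 sets the collapsing rule. Its trigger is "If a subject experiences multiple events that map to a single preferred term"; in that case "the greatest severity grade and strongest investigator assessment of relation to study medication will be assigned to the preferred term for the appropriate summaries". The next sentence deals with gaps: "Should an event have a missing severity or relationship, it will be classified as having the highest severity and/or strongest relationship".

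Several planned outputs use both attributes together. In the final analysis (SAP Section 12) these are "14.3.1.2.1 Treatment-Emergent Adverse Events Related to Vicinium By System Organ Classification, Preferred Term, and Greatest Severity", with subgroup versions up to 14.3.1.2.7, and "14.3.1.6.1 Treatment-Emergent Adverse Events Related to Vicinium by System Organ Classification, Preferred Term, and Severity Group", with frequency cut-off versions up to 14.3.1.6.4. The DSMB package (SAP Section 10) has "Table 6 Treatment-Emergent Adverse Events Related to Vicinium by System Organ Classification, Preferred Term, and Greatest Severity, Safety Population", and the 6-month package (SAP Section 11) repeats it.

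The protocol and the SAP do not describe the relationship scale in the same way. Protocol Section 15.2 has two levels ("Assessment of the relationship of the AE to the study drug by the investigator will be based on the following two definitions": not related and related). SAP Section 3.3.7 refers to five ("attribution of unrelated, unlikely, possible, probable, or definite").

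**The concern.** A table of related events by severity is read as a count of subjects whose drug-related event reached a given grade. That reading holds only if grade and relationship describe the same event. The SAP rule does not ensure this. A mild related event and a severe unrelated one under the same term can merge into a severe related entry.

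The situation is plausible here. Under Protocol Section 12.1 each subject may receive 18 induction instillations and then one every other week up to Week 104, all by catheter. Protocol Section 14 adds cystoscopy every 13 weeks, with biopsies where indicated. The same urinary term could therefore recur in one subject with different causes.

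What is at stake is the accuracy of a descriptive safety count. Safety and tolerability is a listed secondary endpoint. Protocol Section 12.6 also treats related events of Grade 3 or higher as a category with consequences for dosing, so a composite entry may match no dosing record. Protocol Section 15.2 reserves the not-related label for events attributable with certainty to another cause. The rule can in effect override that judgement for the severe event.

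**Working it through.** The documents state no figure on this point, so there is none to reproduce. The check compares two derivations for one subject and one preferred term:

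- **A (SAP wording):** maximum grade over all events, and maximum relationship over all events.
- **B (filter first):** keep the related events only, then take the maximum grade.

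**Step 1. Worked cases**

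| Events under the term | A | B |
|---|---|---|
| Grade 1 related + Grade 3 unrelated | Grade 3 related | Grade 1 related |
| Grade 1 unrelated + Grade 3 related | Grade 3 related | Grade 3 related |
| Grade 3 related + Grade 3 unrelated | Grade 3 related | Grade 3 related |
| Grade 1 related + Grade 1 unrelated | Grade 1 related | Grade 1 related |
| Grade 1 unrelated + Grade 3 unrelated | not in related table | not in related table |

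Only the first case differs.

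**Step 2. All two-event patterns.** Five grades and two relationship levels give 10 event types, hence 10 x 10 = 100 ordered pairs. A false Grade 3+ related entry needs a related event of Grade 1 or 2 (2 types) and an unrelated event of Grade 3 to 5 (3 types), in either order: 2 x 3 x 2 = 12. So 12 of 100 patterns give a false entry under A, and none do under B. This counts patterns; it is not a frequency.

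**Step 3. The missing-value rule.** An unrelated event with missing grade takes the highest severity and can then pair with a mild related event. A mild event with missing relationship is treated as related and can then pair with a severe unrelated one. Both produce the same false pairing under A and neither does under B.

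**Step 4. Illustrative size per urinary term.** False entries = N x q_r x q_u, assuming independence.

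- N = 134, the planned total (Protocol Section 10).
- q_r = share with a related event under the term. The Phase 2 treatment-related rates in Protocol Section 7 are 50% for dysuria and 13% for hematuria. These include all grades, so they run slightly high for mild or moderate events.
- q_u = share with an unrelated Grade 3+ event under the same term. The documents do not give it; 1% to 5% is assumed.

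Dysuria: 134 x 0.50 x 0.01 = 0.67; 134 x 0.50 x 0.05 = 3.35.
Hematuria: 134 x 0.13 x 0.01 = 0.17; 134 x 0.13 x 0.05 = 0.87.

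For scale, Phase 2 reported 3 severe events in 46 subjects, at most 3/46 = 6.5% of subjects across all terms and causes. A rate of 5% for unrelated events under one term would use up most of that, so the low end is more credible.

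**Step 5. Illustrative size among subjects with repeat events.** Assume two independent events per subject and term, with P(Grade 3+) = s and P(related) = r. Neither value is in the documents.

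- False: 2 x r(1-s) x (1-r)s. Genuine: 1 - (1-rs)^2.
- s = 0.02, r = 0.2: false 0.0063, genuine 0.0080, ratio 0.79.
- s = 0.10, r = 0.5: false 0.0450, genuine 0.0975, ratio 0.46.

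Over s = 0.02 to 0.10 and r = 0.2 to 0.5 this gives about 0.6 to 4.5 false entries per 100 subject-term pairs with repeat events, or 0.46 to 0.79 times the number of genuine ones.

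**The case against.** The best defence is the closing phrase of the rule, which limits it to the appropriate summaries. It can be read as greatest severity for severity tables and strongest relationship for relationship tables. The table titles speak of events related to Vicinium, which fits selecting related events and then grading them. A programmer could reasonably do that. The point stands in part: the false pairing is what the literal wording gives, not a certain outcome. But no passage says that the filter comes first, Protocol Section 17.6 does not settle it, and in a table of relationship by severity both attributes are appropriate.

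It is also fair to say that the rule is cautious, like the missing-value rule beside it, that no efficacy result depends on it, and that all events are listed individually. All of this stands and limits the priority. The planned Grade 3+ tables (14.3.1.13.1 to 14.3.1.13.7) do not use relationship, so the pairing cannot create a false entry there. Overall event and serious-event incidence is unaffected.

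A reader might infer three stronger points that the documents do not support:

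- *Maintenance-phase grades are carried into induction rows.* SAP 5.3.1 plans summaries by phase and is silent on whether the maximum is taken within phase. Silence is not a stated rule.
- *Grade 3+ related events are the key safety figure.* No passage says so.
- *Several subjects, or several percentage points of subjects, will be misclassified.* This needs the assumed 1-5% rate. Adding terms together also counts subject-term entries, so one subject may be counted more than once.

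**Conclusion.** Wrong as written; minor priority. On its plain wording, SAP 5.3.1 can place a Grade 3+ Vicinium-related entry in the affected tables when no single event was both. The direction is fixed: severe related toxicity can be overstated, never understated. Only descriptive severity columns change, and the true pairing can be recovered from the listings (16.2.7.1 and 16.2.7.4 in the final analysis, Listing 3 in the DSMB and 6-month packages), though not from the tables.

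That the false pairing can occur rests on no numerical assumption. Its frequency does. The range of 0.2 to 3.4 subject-term entries per urinary term depends on the assumed 1-5% rate, on independence, and on Phase 2 rates carrying over to a trial with a different dosing schedule.

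**What to change.** Replace the sentence in SAP 5.3.1 with:

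> For each table, first select the events that meet that table's filter (treatment-emergent, related, serious, and phase where shown); then count each subject once per preferred term at the greatest grade among the selected events.

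Apply it to the final, DSMB and 6-month tables. This removes the false pairing, including the version that arises through missing values, and settles the question of phase.

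In the same edit, reconcile the two-level relationship scale in Protocol 15.2 with the five-level one in SAP 3.3.7 and state which levels count as related, since the related filter depends on it.

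The cost is one SAP sentence, a clarification of the scale, and a change in the order of two programming steps. No new data are needed.

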### 15.2 Adverse Events

An adverse event (AE) is defined as any untoward medical occurrence in a subject administered a pharmaceutical product and which does not necessarily have to have a causal relationship with this treatment. An AE can, therefore, be any unfavorable and unintended sign (that may include an abnormal laboratory finding), symptom, or disease temporally associated with the use of a medicinal product, whether or not related to the medicinal product. Any worsening of the subject's pre-existing medical conditions will also be considered an AE, unless it is within the normal range of disease fluctuation for that subject. Pre-existing medical conditions that are stable or improve during the study will be recorded as an AE but will not be considered as treatment-emergent adverse events (TEAEs).

The investigator is responsible for reviewing all laboratory results obtained after a subject signs the ICF through 30 days after the last dose of study drug, whether required by this protocol or for other reasons e.g., evaluation of a pre-existing condition, evaluation and management of an AE. Any abnormal value that leads to a change in the subject's management (e.g., dose interruption, dose reduction, the addition of medication, other medical intervention (e.g., blood transfusion), or increased monitoring) or considered by the investigator to be of clinical significance should be recorded as an AE/SAE.

"Progressive disease" should not be recorded as an AE or SAE. Instead, the diagnoses/syndromes, signs, and/or symptoms associated with a subject's disease progressive should be recorded as AEs, or SAEs if they meet the SAE definition.

All AEs will be assessed using the NCI-CTCAE (version 4.03)  
([http://evs.nci.nih.gov/ftp1/CTCAE/CTCAE\\_4.03\\_2010-06-14\\_QuickReference\\_8.5x11.pdf](http://evs.nci.nih.gov/ftp1/CTCAE/CTCAE_4.03_2010-06-14_QuickReference_8.5x11.pdf)).

AEs for which no appropriate CTCAE term exists will be recorded verbatim from the investigator and graded for severity based on CTCAE definitions:

- Grade 1: Mild; asymptomatic or mild symptoms; clinical or diagnostic observations only; intervention not indicated.
- Grade 2: Moderate; minimal, local or noninvasive intervention indicated; limiting age-appropriate instrumental activities of daily living (ADLs)\*.

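### SAP 5.3.1 gives an adverse event with missing severity the top of the CTCAE scale, which is Grade 5 (death), with no cap for subjects who survived

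*SAP*

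**What the plan says.** SAP 5.3.1 has adverse event severity assessed "by the investigator according to the protocol and the CTCAE v 4.03 criteria". SAP 3.3.7 names the same scale: "version 4.03 will be utilized for AE reporting". The sentence at issue in 5.3.1 reads: "Should an event have a missing severity or relationship, it will be classified as having the highest severity and/or strongest relationship", and it applies "for the purposes of summary analyses". The next sentence limits its reach: "For presentation in the data listings, the missing values will be noted".

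SAP 5.3.1 also rolls events up within a subject. Where several map to one preferred term, the term takes the worst grade and the strongest relationship.

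Protocol 15.2 sets the scale: "All AEs will be assessed using the NCI-CTCAE (version 4.03"). It leaves no event outside that scale: "AEs for which no appropriate CTCAE term exists will be recorded verbatim from the investigator and graded for severity based on CTCAE definitions". It then lists Grades 1 to 5. The second highest is "Grade 4: Life-threatening consequences; urgent intervention indicated". The highest, Grade 5, is death.

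**The concern.** Assuming the worst for a missing severity is a familiar convention, and it is sound when the top category means severe. On this scale the top category is an outcome. Whether the subject died of the event is a fact that is recorded elsewhere, so giving that category to a survivor is an error and not a cautious estimate.

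What is at stake is how the safety tables read. Protocol 17.6 plans tables and/or listings of adverse events by death, but the list of final outputs in SAP section 12 has no separate table or listing of fatal adverse events. A reader is therefore likely to take the Grade 5 rows as the count of fatal treatment-emergent events. If relationship is missing on the same record, the event would also be tabulated as related to study drug. In a single-arm trial there is no control rate to put one such row in context.

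**Working it through.** The plan gives no figure to reproduce. The check is a reading of the text, followed by a small illustration.

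**Step 1. What the rule assigns.**
- Scale: CTCAE v4.03, Grades 1 to 5 (SAP 3.3.7 and 5.3.1; Protocol 15.2).
- Imputed value: the highest category on that scale (SAP 5.3.1).
- Highest category: Grade 5, defined as death (Protocol 15.2).

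So a missing severity becomes Grade 5.

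**Step 2. Whether anything stops it.** Neither document has a cap at Grade 3 or 4, an exception for non-fatal events, a row for unknown severity, or another definition of the highest severity. SAP 3.3.4 says that missing data other than dates are generally not imputed, but it gives way where another section specifies otherwise, and 5.3.1 does.

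**Step 3. Where the imputed grade appears.**
- Final tables by greatest severity: 14.3.1.1.x, 14.3.1.2.x (if related), 14.3.1.3 (if it led to discontinuation of study drug) and 14.3.1.4.x (if serious).
- Final tables of Grade 3 or higher events: 14.3.1.13.x.
- Tables 5 to 7 of the DSMB and 6-month packages.
- Not the listings, which show the value as missing.

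**Step 4. Effect of the roll-up.** The rule is worded for a single event, so I take imputation to come before the roll-up. Consider a surviving subject with three episodes of one preferred term: Grade 1, Grade 2 and ungraded.

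| Handling of the ungraded episode | Grade tabulated for the term |
|---|---|
| SAP as written (5) | max(1, 2, 5) = 5 |
| Non-fatal, Grade 4 | max(1, 2, 4) = 4 |
| Non-fatal, Grade 3 | max(1, 2, 3) = 3 |

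In all three rows the subject counts in the Grade 3 or higher tables. Only the first shows a death that did not happen.

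**Step 5. Size per affected subject.** This assumes a denominator of 134, the planned total. SAP section 9 prints percentages without decimals.
- 1 subject: 1/134 = 0.75%, printed as 1%.
- 2 subjects: 2/134 = 1.49%, printed as 1%.
- 3 subjects: 3/134 = 2.24%, printed as 2%.

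The documents give no number of ungraded events, so no expected total can be derived.

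**The case against.** The strongest reply is that this is a gap in wording that may never have an effect. The rule does not name Grade 5, and a sensible programmer might cap it. Protocol 18.2 and 18.3 call for complete eCRFs checked by monitors. Protocol 15.1 has the Medical Monitor follow events continuously, with safety tables and listings each quarter. SAP 3.4 has the final analysis run on cleaned, locked data. Deaths are also captured independently: Protocol 15.3 makes death a seriousness criterion and records the outcome of each serious event, and under 15.1 the DSMB chair receives every SAE report. A Grade 5 row with no fatal report behind it could be traced, because the listings show the grade as missing.

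Most of this stands, and it limits the size of the problem. It does not remove the defect. No cap is written, and SAP section 5 verifies results by independent programming, which offers no protection if both programmers follow the same sentence. If queries resolve every missing grade, the rule is never used; it acts only where they have not.

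Several stronger readings are tempting but not supported:
- **The tables will contain false deaths.** Neither document reports any ungraded event.
- **Every ungraded event adds a false Grade 5 subject.** Events that are not treatment-emergent do not enter these tables, and several ungraded episodes of one term in one subject collapse to one.
- **A mismatch with overall survival would reveal the error.** Under SAP 3.3.7, overall survival counts deaths from any cause at any time, whereas treatment-emergent events stop 30 days after the last dose. The two need not agree.
- **The DSMB would be misled.** It holds listings and SAE reports that would show the discrepancy, and neither document says how complete grading is at an interim cut.

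**Conclusion.** The point holds as a defect in a stated rule. Read literally, SAP 5.3.1 places an ungraded treatment-emergent event in a surviving subject in the category that the protocol defines as death, and lets it replace that subject's real grades for the same term.

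The effect is confined to the safety summary tables. No endpoint, analysis population, hypothesis or sample size is touched. Its size is about 0.7 percentage points in a Grade 5 row per affected subject, if the denominator is 134, and the number of affected subjects is unknown and may be zero. The conclusion rests on two readings: that the highest severity means the top of the CTCAE scale, and that imputation is done event by event before the roll-up. The second bears only on the overriding of graded episodes.

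**What to change.** Amend the sentence in SAP 5.3.1 along these lines: *For summary tables, an adverse event with missing severity is assigned Grade 5 only if a fatal outcome is recorded for that event; otherwise it is assigned Grade 3. Each affected table carries a footnote with the number of events imputed.*

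Grade 3 is one acceptable choice, because it keeps the event in the Grade 3 or higher tables. Grade 4 serves equally well if the worst non-fatal case is wanted. What matters is that the SAP names a non-fatal grade. The rule for missing relationship can stay as it is, since counting an event as related is a legitimate worst case.

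The cost is one sentence and a footnote. No new data are needed, because the outcome of serious events is already recorded on the eCRF (Protocol 15.3). There are two limits. With Grade 3, an ungraded event that was truly Grade 4 shows one grade too low until the query is answered. With either grade, the imputed value still overrides real Grade 1 or 2 episodes of the same term, and the footnote makes that visible.
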